# 10.3. Process evaluation

# 10.3.1. Quantitative element

Data for the quantitative element of the process evaluation will be collected in-store and from cluster RCT participants during home visits.

#### 10.3.2. Qualitative element

Participants in the qualitative element of the process evaluation will be recruited in-store (costumers) or at their place of work (retail sector personnel and intervention implementation professionals). Data will be collected from customers during focus groups in community locations. Data will be collected from retail sector personnel and intervention implementation professionals during interviews at their place of work, or other convenient location.

# 11. PARTICIPANTS - INCLUSION CRITERIA

Separate inclusion criteria are listed for cluster RCT stores and individual participants. The same criteria used to select individuals participants to take part in the cluster RCT will be used to select customers to take part in the qualitative element of the process evaluation. The economic evaluation will use data collected as part of the other elements of the research and no additional new participants will be recruited for it. The quantitative element of the process evaluation will rely solely on analysis of individual level data collected

from all RCT participants, sales data and in-store observations. No separate participants will be recruited for this component.

#### 11.1. Cluster RCT

#### 11.1.1. Stores

Stores included in the research will meet the following criteria:

- Member of one of the 'symbol' groups, e.g. Spar, Londis, Costcutter, Premier, Nisa or Mills Group
- Expressed an interest in taking part in the intervention to the DH implementation team
- Located at least 1km, network distance, from all other study stores
- Located in a lower super output area with an Index of Multiple Deprivation 2007 (IMD) score below the median for the all Government Office regions that study stores are located in
- Located in an urban area as defined by the Department for Environment, Food and Rural Affairs 'Rural Definition' of urban areas (http://www.defra.gov.uk/rural/ruralstats/rural-definition.htm#defn)

If a store is selected for the study that is less than 1km from another study store, replacement sampling will take place.

#### 11.1.2. Individuals

Cluster RCT participants will be recruited in-store and will meet the following criteria:

- Have used the study store on average at least twice per week over the past three months
- Member of a household from which no other member has already been recruited to take part
- Able and willing to give consent to take part in the research
- Age 18 years or older
- Able to communicate in English

### 11.2. Process evaluation (qualitative element)

Members of three stakeholder groups will be selected to take part in the qualitative element of the process evaluation: study store customers, retail sector personnel, and intervention implementation professionals. Customers and retail sector personnel will be recruited from a small number of cluster RCT study stores (both intervention and control).

#### 11.2.1. Stores

Stores will be purposively sampled for inclusion in the qualitative element of the process evaluation from all study stores. They will, therefore, meet the following criteria:

- Study store in cluster RCT
- Purposively sampled to represent different socio-economic locations and sizes of all stores in cluster RCT

# 11.2.2. Customers

Customers taking part in the qualitative element of the process evaluation will meet the same criteria as cluster RCT individual participants, and will be purposively sampled to reflect the socio-demographic composition of individual participants in the cluster RCT recruited from the same store. To avoid drawing cluster RCT individual participants' attention to the intervention, they will be excluded from the qualitative process evaluation. Thus, there will be no overlap between cluster RCT individual participants and those in the qualitative element of the process evaluation will, therefore, meet the following criteria:

- Have used a cluster RCT study store on average at least twice per week over the past three months
- Member of a household from which no other member has been recruited to take part in cluster RCT
- Able and willing to give consent to take part in the research
- Age 18 years or older
- Able to communicate in English
- Not taking part in the cluster RCT
- Purposively sampled to reflect the socio-demographic composition of individual participants in the cluster RCT recruited in the same study store

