#### 11.2.3. Retail sector personnel

Members of staff at study stores selected to take part in the qualitative element of the process evaluation will be purposively sampled to reflect store managers and owners, in-store Fresh Food Champions (see section 18.1.2 for definition), and other staff. They will, therefore, meet the following criteria:

- Work at study store selected for inclusion in the qualitative element of the process evaluation
- Able and willing to give consent to take part in the research
- Age 18 years or older
- Able to communicate in English
- Purposively sampled to reflect store managers and owners, in-store Fresh Food Champions, and other staff

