#### 12. PARTICIPANTS - EXCLUSION CRITERIA

None, beyond inclusion criteria listed.

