# 21.1.4. Recruitment of individual participants

Based on previous research, we estimate that around 40% of individuals invited to take part in the study will agree. Potential participants will be recruited in-store by trained NatCen fieldworkers who will approach adult shoppers and invite them to take part in a short screening questionnaire to confirm the inclusion criteria. If these are met, the research will be explained and individuals will be invited to take part. Those who express interest will be given a written information sheet and asked to provide contact details so a home visit from a trained NatCen fieldworker can be arranged.

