# 24.1. Cluster RCT

#### 24.1.1. Stores

It will be impossible to blind store staff to the group they have been allocated to, and no attempt will be made to do this. Store managers will be informed whether they have been allocated to the control or intervention group after baseline data collection via a letter.

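### Employees, managers and owners who shop in their own study store are eligible for the cluster RCT, although they cannot be kept unaware of the intervention

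*Protocol*

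**What the plan says.** Section 11.1.2 lists five criteria for individual RCT participants. They cover store use, one person per household, consent, age 18 or over, and English. The store-use criterion reads "Have used the study store on average at least twice per week over the past three months". None concerns employment at the store, and section 12 gives the exclusion criteria as "None, beyond inclusion criteria listed". Under section 21.1.4, recruitment is by fieldworkers "who will approach adult shoppers and invite them to take part in a short screening questionnaire to confirm the inclusion criteria".

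On awareness, section 24 says that at baseline neither participants nor fieldworkers are told what the intervention is or which arm a store is in. Section 24.1.2 adds that individuals are not told the outcome of interest. Both accept that participants may notice changes by 12 months. For store personnel, section 24.1.1 says: "It will be impossible to blind store staff to the group they have been allocated to". Managers receive the allocation by letter after baseline data collection.

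On the interviews, section 11.2.2 says: "To avoid drawing cluster RCT individual participants' attention to the intervention, they will be excluded from the qualitative process evaluation". It concludes that "there will be no overlap between cluster RCT individual participants and those in the qualitative element of the process evaluation" and gives customers the criterion "Not taking part in the cluster RCT". The list for retail personnel in section 11.2.3 opens with "Work at study store selected for inclusion in the qualitative element of the process evaluation" and has no matching criterion. Nor does the list for implementation professionals in section 11.2.4.

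**The concern.** The protocol takes trouble to keep RCT participants from learning what is being studied, because the primary outcome is change in a diary that they complete themselves. People who run or work in a study store are a group for whom this cannot succeed, and nothing in the RCT criteria keeps them out.

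They also differ in kind from a customer who happens to notice a new display. Under section 18.1.2 the Fresh Food Champion is a member of staff who receives a tutorial and looks after the branded units, so one person could both deliver the intervention and supply the primary outcome. Under section 18.1.1 the retailer pays most of a toolkit cost of £15,000 to £20,000, with an average of £3,000 coming from the Department of Health. An owner therefore has a stake in the result. If such participants record or eat more fruit and vegetables in intervention stores, the arm difference moves for reasons unrelated to the intervention's effect on customers. The multilevel model corrects standard errors for clustering; it does not remove a bias of this kind.

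**Working it through.** **1. Can store personnel enter the RCT?** An adult employee, manager or owner who has shopped in the store twice a week for three months, consents, speaks English and is the first in the household to be recruited meets all five criteria in 11.1.2. Section 12 adds nothing. Screening under 21.1.4 checks those criteria only. They are therefore eligible.

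**2. What would they know, and when?**
- Before the baseline diary: stores must have expressed interest in the intervention to the implementation team (11.1.1). Managers then receive a letter, an information sheet, a call and a visit, and give consent (21.1.2). The milestones in section 39 have all store consents in place by the end of November 2010, and all individual consents by the end of April 2011. Managers and owners can therefore know the intervention before completing a baseline diary.
- After baseline: the arm is disclosed to managers, and no attempt is made to blind staff (24.1.1).
- During follow-up: in intervention stores a staff member acts as Fresh Food Champion (18.1.2).

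Knowledge before baseline precedes disclosure of the arm, so it should affect both arms alike. Knowledge and delivery after baseline differ by arm, and these are what could bias the contrast.

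**3. Does the interview rule cover them?** Section 11.2 defines the qualitative element as three groups: customers, retail sector personnel and implementation professionals. The exclusion in 11.2.2 is from the whole qualitative process evaluation. Taken together, an RCT participant may not be interviewed as staff. The rule sits under the customer heading and is not repeated in 11.2.3 or 11.2.4.

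**4. Scale of the design.** Inputs from 14.1.1: difference 0.5 portions (40 g), SD 2.1 portions, 80% power, two-sided 5%, ICC 0.01, 25 per store at follow-up, 38 per store at baseline, 28 stores.
- n per arm = 2 × (1.96 + 0.84)² × 2.1² / 0.5² = 276.6, so 277 per arm and 554 in total.
- Design effect = 1 + (25 − 1) × 0.01 = 1.24; 554 × 1.24 = 687. The protocol states 692, so its figure is reproduced to within 1%.
- Implied standard error of the arm difference = 40 / 2.8 = 14.3 g.
- Baseline total = 38 × 28 = 1064, as stated.

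**5. Illustrative shift.** The documents give neither the number of staff who would be recruited nor the size of any over-reporting. Assume k staff in every intervention store, each showing 80 g (one portion) more change, with no counterpart in control stores. Shift = 80 × k / 38.
- k = 0: 0 g.
- k = 1: 80 × 1/38 = 2.1 g, which is 5% of 40 g and 0.15 standard errors.
- k = 2: 80 × 2/38 = 4.2 g, which is 11% of 40 g and 0.29 standard errors.
- If all staff were retained while the store total fell to 25, the last two become 80 × 1/25 = 3.2 g and 80 × 2/25 = 6.4 g (16% of 40 g, 0.45 standard errors).

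**6. Ceiling on interview overlap if the rule were overlooked.** 16 stores × 2 interviews (14.1.2) = 32 people, or 32/1064 = 3.0% of the baseline sample. At most 8 × 2 = 16 of them would be in intervention stores.

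**The case against.** **Staff are not who is approached.** Fieldworkers approach adult shoppers, sampling follows footfall estimated from sales data (21.1.3), the RCT information sheet and consent form are titled for customers (40.1), and the protocol treats customers and retail personnel as separate groups. This stands in part: it makes enrolment of staff less likely and the realistic number may be near zero. It does not prevent it, since an employee buying groceries is a shopper who passes every screening item.

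**The trial is already called unblinded.** Section 24.1.2 accepts that regular users of an intervention store will probably notice changes. This also stands in part. The concession concerns what participants may notice by 12 months. It does not cover participants who know the intervention before baseline, are told the arm, or deliver the intervention.

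**Staff who are regular users belong to the target population.** Section 21.1.3 defines that population by the inclusion criteria, so removing staff is a choice. That is fair, but the protocol neither makes nor defends that choice, and including them conflicts with its own aim in section 24.

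**A stronger reading is tempting:** because 11.2.3 lacks the bar given to customers, a reader might infer that staff in the RCT may also be interviewed at about 8 months, and that the no-overlap statement fails. The documents do not support this. If the exclusion in 11.2.2 is general, it is itself the bar. If its heading confines it to customers, the customer criterion delivers it. On neither reading does the protocol contradict itself; the missing criterion in 11.2.3 is a drafting gap.

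**Conclusion.** The point holds as one about RCT eligibility. The criteria admit employees, managers and owners of study stores who shop there regularly, and these people cannot be kept unaware of the intervention as sections 24 and 24.1.2 intend. The no-overlap rule is sound as written.

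Any bias is probably small and may be zero. The illustrative shift of about 2 to 4 g, or up to 6.4 g with full retention of staff, rests wholly on assumptions: one or two staff in every intervention store, a full extra portion each, and no offset in controls. Even then it is less than half of one standard error. It would not overturn the primary analysis. Under those assumptions it favours the intervention, and analysis cannot remove it if employment is not recorded. That justifies an inexpensive correction before recruitment begins, and nothing more.

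**What to change.** Add to section 11.1.2: 'Not an employee, manager or owner of a study store.' Ask this in the in-store screening questionnaire already planned in 21.1.4. The cost is one question and a few recruits who can be replaced, so the 38 per store in 25.1.2 is unaffected. The result then applies to customers and not to store personnel, which fits the aim of the trial. If the sponsor prefers to keep personnel eligible, 11.1.2 should say so openly.

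For consistency only, repeat "Not taking part in the cluster RCT" in sections 11.2.3 and 11.2.4, so that whoever selects interviewees sees the rule where it applies. The exclusion should not extend to household members of store personnel: nothing in the documents supports that.

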#### 11.2.3. Retail sector personnel

Members of staff at study stores selected to take part in the qualitative element of the process evaluation will be purposively sampled to reflect store managers and owners, in-store Fresh Food Champions (see section 18.1.2 for definition), and other staff. They will, therefore, meet the following criteria:

- Work at study store selected for inclusion in the qualitative element of the process evaluation
- Able and willing to give consent to take part in the research
- Age 18 years or older
- Able to communicate in English
- Purposively sampled to reflect store managers and owners, in-store Fresh Food Champions, and other staff

#### 11.2.4. Intervention implementation professionals

This group will include members of the DH implementation team, key decision makers from symbol groups, symbol group regional managers involved in the intervention (see section 18.1.3 for definition) and any other professionals involved in intervention implementation.

- Member of key stakeholder group
- Able and willing to give consent to take part in the research
- Age 18 years or older
- Able to communicate in English

#### 12. PARTICIPANTS - EXCLUSION CRITERIA

None, beyond inclusion criteria listed.

#### 13. PARTICIPANT INFORMATION MATERIAL

See appendices (section 40).

#### 14. TARGET NUMBER OF PARTICIPANTS AND SAMPLE SIZE CALCULATIONS

Cluster RCT: 2660 individuals across 28 stores. Also: 18 focus groups with consumers, 32 interviews with retail sector personnel and 10 interviews with implementation professionals.

Sample sizes are described for stores and individual participants taking part in the cluster RCT and the qualitative element of the process evaluation. Sample size for the economic evaluation and quantitative element of the process evaluation will be as for the cluster RCT.

# 14.1.1. Cluster RCT

The sample size calculation was based on a t-test of the mean difference between groups in change in FFV consumption between baseline and 12 months. As the data are clustered at the c-store level, individual level sample size was multiplied by a design effect to retain statistical power. The study is powered to detect a mean difference in change of FFV intake of 40g (0.5 portions) per day. This represents an increase of around 20% above current population levels(4) and is similar to the change seen in other community intervention studies.(11, 12)

There are two published UK studies which provide data on change in FFV intake from baseline to 12 months following retail changes.(13-15) Both were used to provide estimates of the standard deviation of change in FFV intake from baseline to 12 months for intervention and control groups. The pooled estimates of the standard deviations of the change were 1.8 (95% CI: 1.66-1.96) and 2.2 (95% CI: 2.06-2.37). We were also able to access unpublished data, supplied by the MRC Human Nutrition Research Centre in Cambridge, from a method comparison study of four day food diaries and repeated 24hr recalls conducted over four consecutive days.(16) From this study the standard deviation for FFV intake at a single time point was 2.1 (95% CI: 1.98 -2.23). There are no published data on the intraclass correlation (ICC) for the change in FFV intake at the c-store level. However, data from Newcastle provide an ICC for actual FFV intake at the postcode level of 0.01(7) and 'typical' values of ICCs in community randomised trials have been found to be small (usually less than 0.01 and often near 0.001).(17) Given most of the unexplained variation in FFV intake in the Newcastle study was at the individual level, and since similar observations were made for all

dietary outcomes,(7) this ICC has been used as a guide in the calculation of possible design effects. Further, the c-stores included in this study will be sampled from locations with IMD scores below the median for the study region, thus restricting the variation between clusters in terms of IMD – associated with FFV intake in the Newcastle study.(7) Given these considerations, sample size calculations were performed using standard deviations across the range 1.6 to 2.4 with ICCs of 0.005, 0.01 and 0.02.

We calculate that a total achieved sample size at follow up of 692 individual participants and 28 c-stores (14 intervention and 14 control) is required to detect as statistically significant a mean difference in the change in FFV intake between study groups of 40g (standard deviation of the differences 2.1 portions, 80% power, 5% significance level, two-sided test, ICC 0.01). This equates to 25 individual participants per store. Assuming 35% attrition between baseline and follow up,(15) the total number of individual participants recruited at baseline per c-store increases to 38 and the total sample size at baseline to 1064. Assuming a recruitment rate of 40%, (similar to that in previous work; [name], personal communication), the total number of individuals that we will invite to take part will be approximately 2660.

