#### 28.1.2. Statistical analysis

For the primary outcome measure, the null hypothesis is that there is no difference in mean change in FFV intake from baseline to 12 months between individuals clustered around intervention and control stores. The alternative hypothesis is that the mean difference in the change between the two groups is not equal to zero. The null hypothesis will be tested using a multilevel model with random components for individuals and c-stores, and will be adjusted for baseline FFV intake and randomisation stratification variables. The multilevel model takes account of the clustering of individuals at the c-store level and adjusts standard errors appropriately. The result of this analysis will be presented as a 95% CI for the (adjusted) mean difference in the change in FFV intake between the two groups.

A multilevel modelling approach also allows variation in change in FFV intake to be partitioned in to store and individual levels. It permits the inclusion of characteristics of individuals and stores that are known (or hypothesised a priori) to be associated with the outcome of interest. Inclusion of such terms may reduce the estimate of the standard deviation of the effect and hence provide a more precise estimate of the effect of the intervention. The primary analysis will be by intention to treat. If necessary, a per-protocol analysis will also be performed, only including data from those stores that have complied with the intervention.

Exploratory analyses that incorporate interaction terms within and between levels and random coefficient terms at the store level will attempt to tease out "what works for whom, in what circumstances". However, formal hypothesis testing will be restricted to the primary outcome for which the study has been powered. All other hypothesis testing will be informal and interpreted as such.

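### The stated 80% power ignores that only 28 stores are randomised: on store-level degrees of freedom the test used for sizing has about 77%, and its SD of 2.1 is not traced to a change SD

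*Protocol*

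**What the plan says.** Protocol section 14.1.1 describes the method in two steps: "The sample size calculation was based on a t-test of the mean difference between groups in change in FFV consumption between baseline and 12 months", after which "individual level sample size was multiplied by a design effect to retain statistical power". The trial is "powered to detect a mean difference in change of FFV intake of 40g (0.5 portions) per day". The result is 692 participants at follow-up in 28 stores, 14 per arm, about 25 per store, under these conditions: "standard deviation of the differences 2.1 portions, 80% power, 5% significance level, two-sided test, ICC 0.01".

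The same section gives two pooled estimates of the SD of change, 1.8 (95% CI 1.66 to 1.96) and 2.2 (95% CI 2.06 to 2.37). From a separate method-comparison study it reports that "the standard deviation for FFV intake at a single time point was 2.1". It says that SDs from 1.6 to 2.4 and ICCs of 0.005, 0.01 and 0.02 were examined, but reports the result for one combination only.

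Sections 9.1.1 and 22 make the store the unit of randomisation. For the primary analysis, section 28.1.2 states: "The null hypothesis will be tested using a multilevel model with random components for individuals and c-stores", adjusted for baseline intake and the stratification variables.

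**The concern.** A design effect enlarges the variance of the arm difference to allow for clustering. It does not change the reference distribution. When 28 stores are randomised, the variance of the arm contrast is estimated from variation between stores, so a test that respects the design has 28 − 2 = 26 degrees of freedom rather than several hundred. Section 14.1.1 mentions no allowance for this, so 80% would overstate the power of the very test on which the calculation rests.

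The second problem is where the SD comes from. A calculation on change needs the SD of change. The value used carries that label, but in the text that precedes it 2.1 appears only as the SD of intake at one time point. A reader cannot tell whether it was chosen as a compromise between 1.8 and 2.2 or carried over from the wrong quantity.

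At stake is whether the one power figure in the protocol can be relied on, and whether it says anything about the analysis that will be run.

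**Working it through.** **Inputs (section 14.1.1).** Difference d = 0.5 portions; SD 2.1; ICC 0.01; two-sided 5%; N = 692; 28 stores. The protocol does not print its design-effect formula; the usual 1 + (m − 1) × ICC is assumed.

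**Reproducing the plan's figure.**
- Individual-level size per arm: 2 × (2.1 × (1.960 + 0.842) / 0.5)² = 277, or 554 in total. A t-test gives 278 per arm, or 556.
- Design effect at 25 per store: 1 + 24 × 0.01 = 1.24. Then 554 × 1.24 = 687 and 556 × 1.24 = 689, both within 1% of 692. (The baseline target less attrition, 1064 × 0.65 = 691.6, also rounds to 692.)
- In reverse: m = 692/28 = 24.7; design effect 1.237; SE = 2.1 × √(4 × 1.237/692) = 0.178; noncentrality 0.5/0.178 = 2.82. Power is 80.4% on a normal reference and 80.3% on t with 690 df.

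So N = 692 and 80% follow from the stated method.

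**Same standard error, store-level df.** With the same noncentrality and a noncentral t on 26 df, power is 77.3% at N = 692 and 77.7% at 25 per store (N = 700). As a gauge of size, 80% would be regained with 30 stores of about 25 (80.3% to 80.7%) or with 28 stores of 27 analysed (80.1%).

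**Effect of the SD (N = 692, ICC 0.01).**

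| SD | Where it appears in section 14.1.1 | Normal reference | 26 df |
|---|---|---|---|
| 1.8 | smaller change-SD estimate | 90.7% | 88.5% |
| 2.1 | value used; single-time-point SD | 80.4% | 77.3% |
| 2.2 | larger change-SD estimate | 76.7% | 73.5% |

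From 80.4% to 73.5%, about 4 points come from moving the SD to 2.2 and about 3 from the degrees of freedom.

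**Effect of the ICC (SD 2.1, 26 df, N = 692).** Power is 81.3% at ICC 0.005 and 70.0% at ICC 0.02, two of the values that the protocol says it examined.

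**Planned baseline-adjusted model, under an assumption.** Suppose the single-visit SD is 2.1 at both visits.
- Implied correlation: 1 − (change SD)²/(2 × 2.1²), which is 0.50 for a change SD of 2.1 and 0.45 for 2.2.
- Residual SD after adjustment: 2.1 × √(1 − correlation²), which is 1.82 or 1.87.
- Power on 26 df, keeping ICC 0.01: 87.9% or 85.9%.

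**The case against.** The strongest reply has three parts.

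First, the sample size is not miscalculated: it follows from the method the protocol declares, and the omitted refinement is worth about 3 points, or one more pair of stores. That stands. The fault is in the reference distribution behind the 80%, not in the arithmetic.

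Second, 77% belongs to an unadjusted change-score test that will not be the primary analysis. Section 28.1.2 adjusts for baseline intake, which should reduce residual variance. That also stands, and it rules out the tempting conclusion that the trial is underpowered. On the assumption worked through above, the planned model exceeds 80%. But the protocol makes no such calculation, so its 80% does not describe that model either.

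Third, 2.1 lies between the two change-SD estimates and inside the confidence interval of the larger one, and a change SD equal to the single-visit SD is what a correlation of 0.5 would give. So 2.1 is a plausible value. The objection answers whether it is reasonable, not where it came from, and the protocol does not say.

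A reader might also infer that the primary test will have an inflated type I error. The documents do not support this: section 28.1.2 names no reference distribution, and the choice of degrees-of-freedom method can properly be left to a statistical analysis plan that is not at hand. Nor do they support a specific figure below 26 df. Section 21.1.1 leaves the deprivation and size strata to be decided, and section 28.1.2 does not say that pairs will be fitted.

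**Conclusion.** The point holds in a limited form. For the test on which the trial was sized, the stated 80% is a large-sample figure; on the 26 degrees of freedom that 28 stores allow, power is about 77% (77.3% to 77.7%). This rests on the protocol's own inputs, the standard design-effect formula and equal store sizes.

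The unexplained SD is a supporting point. It matters more to the result than the degrees of freedom do, but in both directions: 88.5% at one of the protocol's change-SD estimates and 73.5% at the other. It would be wrong to report only the lower figure, or to attribute the whole fall to the number of stores.

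The power of the planned primary analysis cannot be read from the protocol. It may well be above 80%; the 86% to 88% range depends on an assumed SD of 2.1 at both visits. The consequence is a power statement that needs correcting, not a design that needs enlarging.

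**What to change.** In section 14.1.1:

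1. Restate power for the unadjusted change-score test on store-level degrees of freedom. For 692 participants in 28 stores at ICC 0.01 on 26 df, this is about 77% at SD 2.1, with 88.5% and 73.5% at the two change-SD estimates of 1.8 and 2.2.
2. Say where 2.1 comes from. If it is a working value between the two change-SD estimates, say so; if it is the single-time-point SD, correct the label and justify its use for change.
3. Add the power of the planned baseline-adjusted model on store-level degrees of freedom, stating the assumed correlation between baseline and follow-up intake.

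The cost is a short recalculation and a few sentences. The figure for the sizing test becomes slightly less favourable; the figure for the planned analysis may become more so. The number of stores, recruitment and the primary analysis stay as they are.
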